### 3.4 RANDOMIZATION

The right eye of each subject will be randomly allocated to receive either GS010 or sham treatment in a 1:1 allocation ratio. The fellow (left) eye will receive the treatment not allocated to the right eye. Therefore, each subject will receive GS010 in one eye and sham treatment in the fellow eye. Prior to randomization, each subject's best- and worst-seeing eye will be determined. Efron's minimization method will be used in the randomization process to balance as much as possible the two treatment groups (GS010 and sham) in the best-seeing eyes.

To enroll a subject (Visit 1), the Investigator will call an interactive response system (IRS) and provide brief details about the subject to be enrolled. Each subject will receive a subject number assigned at screening, which will serve as the subject identifier throughout the study. The subject number will be required in all communication between the Investigator (or designee) and the IRS regarding a particular subject. Subject numbers will be tracked via the IRS.

To randomize a subject (Visit 2), the Pharmacist (or designee) will call the IRS and provide brief details about the subject to be randomized. Eligible subjects will be randomized in a 1:1 ratio (right/left eye), taking into account the Efron's minimization method, using the IRS.

The IRS User Guide will describe the steps of the randomization process from the subject's screening up to before IVT injection.

An algorithm with a testing hierarchy will be employed prior to randomization to determine the best- and worst-seeing eye of each subject, as follows:

1. ETDRS visual acuity score for subjects able to read the ETDRS chart. The eye with the higher ETDRS score is the best-seeing eye. For subjects who cannot read the ETDRS chart ("off chart" subjects) a standard study procedure will be used to determine visual acuity based

on counting fingers at a given distance. The eye with the best visual acuity based on this method is the best-seeing eye. If one eye of a subject is able to read letters on the ETDRS chart and one eye cannot, the eye able to read the ETDRS chart is the best-seeing eye.

2. SD-OCT parameters (to be used if there is no inter-eye difference based on Criterion 1):

- i) The initial SD-OCT parameter will be the total volume of the RGC layer of the macula. The best-seeing eye will have the greater volume and quadrant thickness, unless there is macula edema. A difference of  $\geq 5\%$  is considered significant to determine greater volume.
- ii) The second SD-OCT parameter (to be used if there is no inter-eye difference in criteria 2i) will be the combined volume of the RGC layer of the inner and outer nasal quadrants of the macula. The best-seeing eye will be the eye with greater volume. A difference of  $\geq 5\%$  is considered significant to determine greater volume.

3. Contrast sensitivity measured with the Pelli-Robson chart (to be used if there is no inter-eye difference in criteria 1 or 2). The eye with the best Log CS (contrast sensitivity) score is the best-seeing eye.

4. If the best-seeing eye is not possible to be determined based on any of the criteria in the algorithm above, the masked investigator will determine the best-seeing eye based on the totality of the Visit 1 vision testing results and subject testimony.

Perceptive Solution, an IRS company, will be responsible for the randomization code generation and actual randomization.

## 4. STUDY VARIABLES AND COVARIATES

### 4.1 PRIMARY VARIABLE

The primary endpoint will be the ETDRS visual acuity (quantitative score) at Week 48 after IVT injection. The subjects' LogMAR scores, which are derived from the number of letters they read on the ETDRS chart, will be used for statistical analysis purposes. LogMAR scores for subjects unable to read the ETDRS chart (i.e. off-chart subjects) will be obtained per the pre-defined Standard Operating Procedure and the protocol. The change from baseline in each eye will be the primary response of interest.

### 4.2 SECONDARY VARIABLES

#### 4.2.1 Efficacy

- Measure of parameters, including RGC layer, INL, ONL thickness/volume, RNFL thickness, and topographical maps of these anatomical regions, obtained with high resolution SD-OCT of the posterior pole and optic nerve at Week 48 and Week 96.

- ETDRS visual acuity (quantitative score) over the follow-up period and at Week 96 after IVT injection. Change from baseline of the LogMAR scores will be used for statistical analysis purposes.
- Response status to treatment at week 48 and 96 after IVT injection.
- Mean Deviation (MD) in decibels of sensitivity and Foveal Threshold Sensitivity will be used at Week 48 and Week 96.
- Measure of contrast sensitivity with the Pelli-Robson chart at Week 48 and Week 96.
- Measure of color vision with the Farnsworth-Munsell 100 Hue color vision test at Week 48 and Week 96.

#### 4.2.2 Safety

- Adverse events (AEs) and serious adverse events (SAEs), including those that are treatment-emergent and non-treatment-emergent, throughout the study period and at each study visit. Incidence and severity of systemic and local (ocular) AEs and SAEs will be determined at each clinical site and for the entire study cohort.

### 4.3 PREDETERMINED COVARIATES AND PROGNOSTIC FACTORS

RGC layer, INL, ONL thickness/volume and topographical maps of these anatomical regions, best or worst-seeing eye (eye status) as determined prior to randomization and duration of vision loss at the time of treatment could be significant prognostic factors for the treatment effect. Sensitivity analysis will be performed for RGC layer thickness/volume and topographical map and eye status (best or worst-seeing eye) and duration of vision loss at the time of treatment by including them in the primary model as a covariate.

## 5. DEFINITIONS

### 5.1 STUDY DAY

All study days on or after the treatment administration will be calculated as date of assessment minus date of treatment administration +1. Study days before the treatment administration will be calculated as date of assessment minus date of treatment administration. In case of missing or incomplete dates no study days will be calculated.

### 5.2 BASELINE

The baseline value is defined as the last non-missing value prior to the start time of treatment administration (Visit 3). If assessment and treatment administration occur on same day and time is not captured, it will be considered as baseline. For OCT parameters baseline is defined as average of Visit 1 and Visit 2 assessments.

### 5.3 CHANGE FROM BASELINE

The change from baseline value is defined as the value at a given time point minus the baseline value.

### 5.4 DERIVED VARIABLES

#### ETDRS Score and LogMAR (on chart and off chart)

ETDRS score is calculated by the examiner and written on the source documents and entered in the eCRF.

LogMAR (on chart and off chart) will all be derived in eCRF from the Snellen/decimal acuity.

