3 STUDY ENDPOINTS

3.1 Primary

The primary endpoint will be the ETDRS visual acuity (quantitative score) at Week 48 after IVT injection. The subjects' LogMAR scores, which are derived from the number of letters they read on the ETDRS chart, will be used for statistical analysis purposes. The change from baseline in each eye will be the primary response of interest.

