7.3.1 Visual Acuity

Enrolled subjects will include those able to read letters on the ETDRS chart (“on-chart” subjects) and those unable to read letters on the ETDRS chart but able to count fingers of the examiner at a given distance (“off-chart” subjects). On-chart subjects will have visual acuity measured with the ETDRS chart and an ETDRS score will be calculated. On-chart subjects will also have a Snellen acuity obtainable from the number of lines read on the ETDRS chart.

Off-chart subjects included in the study must maintain the visual ability to allow them to count fingers of the examiner as per the selection criteria. Off-chart subjects will not have an ETDRS score or a Snellen acuity obtainable from the ETDRS chart. Snellen acuity will be obtained utilizing the measured distance at which the subject was able to count the fingers of the examiner and a standardized formula available at ([Karanjia 2014](#)):

<http://www.countfingers.com/>

The Snellen acuities of on-chart and off-chart subjects will be converted to LogMAR for statistical analysis. Snellen acuities will be transformed to LogMAR using the standard formula available at:

<http://www.myvisiontest.com/logmar.php>

Additionally, 1 ETDRS line is considered equivalent to 0.1 LogMAR.

The visual testing at Visit 4 will be conducted for safety purposes and will not be analyzed as efficacy data (see [Section 7.6.3](#)).

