## Subject Responder

Responder, at week 48 and also at week 96, will be defined as a subject whose ETDRS score of the treated eye is at least 15 letters better than the sham eye *or* whose treated eye has a LogMAR acuity of at least 0.3 LogMAR better than the sham eye. Early discontinuations (prior to W48 for the primary endpoint) will be considered as non responder. For week 96 two analyses will be performed: One for completers and one for subjects who don't have the Week 96 value available. If the week 96 visual acuity score is not available, then the previous visit value will be used.

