## ETDRS/LogMAR and on-chart and off-chart:

- I. 1 ETDRS line = 5 letters
- II. 1 ETDRS line = 0.1 LogMAR
- III. 0.1 LogMAR = 5 ETDRS letters
- IV. 15 ETDRS letters = 0.3 LogMAR

V. A less positive/more negative LogMAR is an improvement of vision

VI. An increase in the number of ETDRS letters read is an improvement of vision

On-Chart subjects: defined as being able to read at least 3 ETDRS letters on a single line on the ETDRS chart at either 4 or 1 meters

- a. Have an obtainable Snellen equivalent obtained directly from ETDRS chart
- b. Each Snellen equivalent is assigned a LogMAR value

Off-chart Subjects: defined as a subject who cannot read at least 3 ETDRS letters on a single line of the ETDRS chart at either 4 or 1 meters and thus have no Snellen equivalent obtainable from ETDRS chart

- c. These subjects are categorized as able to either count fingers (CF), detect hand motion (HM), detect light perception (LP) or are no-light perception (NLP)
- d. For those categorized as either CF or HM a method for deriving LogMAR visual acuity is pre-specified
- e. The distance at which CF/HM vision was obtained is recorded per the standard operating procedure
- f. Study database derives the LogMAR based on this distance and the finger/hand dimensions of the examiner, per pre-specified method.

[figure not shown]

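### The primary LogMAR is defined from letters read but derived from Snellen lines. This barely affects the primary, but it lets some 11- to 14-letter differences count under the secondary subject-responder rule.

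*SAP*

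**What the plan says.** **Endpoint text.** Protocol 3.1 says that the LogMAR scores used for analysis are ones "which are derived from the number of letters they read on the ETDRS chart". SAP 4.1 repeats this: "LogMAR scores, which are derived from the number of letters they read on the ETDRS chart". It refers to a Standard Operating Procedure only for off-chart subjects.

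**Operational text.** Protocol 7.3.1 states: "On-chart subjects will also have a Snellen acuity obtainable from the number of lines read on the ETDRS chart". It continues: "The Snellen acuities of on-chart and off-chart subjects will be converted to LogMAR for statistical analysis". SAP 5.4 (ETDRS Score and LogMAR) agrees: "LogMAR (on chart and off chart) will all be derived in eCRF from the Snellen/decimal acuity". For on-chart eyes, the later part of SAP 5.4 on ETDRS/LogMAR adds: "Each Snellen equivalent is assigned a LogMAR value". The ETDRS letter score is also entered in the eCRF, but it is not named as the source of LogMAR.

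**Scale.** SAP 5.4 sets one line equal to 5 letters and to 0.1 LogMAR, and 15 letters equal to 0.3 LogMAR.

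**Responder rule.** Under SAP 5.4 (Subject Responder), a subject responds if the treated eye's letter score leads the sham eye's by 15 or more. The alternative limb, joined by *or*, is a subject "whose treated eye has a LogMAR acuity of at least 0.3 LogMAR better than the sham eye".

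**The concern.** On the SAP's own equivalences, letter scoring moves in steps of 0.1/5 = 0.02 LogMAR and line scoring in steps of 0.1. The endpoint sections describe the first and the derivation sections produce the second. A reader of SAP 4.1 alone would misstate what the primary analysis uses.

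Two things could follow. First, rounding to lines adds measurement error to the primary change from baseline. Second, the two limbs of the subject-responder rule are meant to be the same bar on two scales, but they stop being so when one scale is rounded. Because the limbs are joined by *or*, every lead of 15 letters already counts, and the rounded limb can only add subjects who fall short of 15.

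Timing matters as well. Protocol Appendix V allows no SAP amendment once the randomization code is broken, and the study is unmasked for the Week 48 analysis (Protocol 12.6, SAP 7.1).

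**Working it through.** **1. Reproduce the planned power (SAP 3.3).** Inputs: difference 0.3 LogMAR, SD of the between-eye difference in change 0.594, 36 subjects, two-sided alpha 0.05 (SAP 9.5.1).

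Noncentrality = 0.3/0.594 × √36 = 3.03 on 35 degrees of freedom, which gives power of 83.8%. The SAP states 84%, so the figure reproduces.

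**2. Cost of line rounding on the primary.** The between-eye difference in change uses four readings: two eyes, each at baseline and Week 48. With uniform rounding error:

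- Per reading, the variance is 0.1²/12 and the SD is 0.029.
- Over four readings, the variance is 4 × 0.1²/12 = 0.0033 and the SD is 0.058.
- Relative to 0.594² = 0.353, this is 0.0033/0.353 = 0.9%.

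The documents do not say how the Phase I/II acuity behind 0.594 was scored, so both cases are shown. Both allow for the small rounding in letter scoring itself (0.02 steps).

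| If 0.594 was | Line-scored SD and power | Letter-scored SD and power |
|---|---|---|
| letter-scored | 0.597, 83.5% | 0.594, 83.8% |
| line-scored | 0.594, 83.8% | 0.591, 84.1% |

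The difference is about 0.3 points either way. In the second case nothing is lost against the plan.

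**3. What 0.3 LogMAR means under line scoring.** Assumptions: both eyes on-chart, letters read in order, 5 letters and 0.1 LogMAR per line. Suppose a line is credited once *t* of its 5 letters are read. An eye with *L* letters then has floor((*L* + 5 − *t*)/5) lines. Let *r* (0 to 4) be the remainder of (*L* + 5 − *t*)/5 for the sham eye. If the treated eye reads *d* more letters, it leads by floor((*r* + *d*)/5) lines. It leads by three or more when *r* + *d* ≥ 15.

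| Letters apart (*d*) | Qualifying *r* | Share of starting scores |
|---|---|---|
| 10 or fewer | none | 0% |
| 11 | 4 | 20% |
| 12 | 3–4 | 40% |
| 13 | 2–4 | 60% |
| 14 | 1–4 | 80% |
| 15 or more | all | 100% |

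The table does not depend on *t*; enumeration for *t* = 1 to 5 gave the same shares. An exact three-line lead covers 15 ≤ *r* + *d* ≤ 19, that is, 11 to 19 letters.

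Example with *t* = 3: a sham eye at 7 letters has 1 line, and a treated eye at 18 letters has 4. They are 11 letters apart, scored as 0.3 LogMAR, and the subject is a responder. On letter scoring the same lead is 11 × 0.02 = 0.22 LogMAR, and the subject is not.

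**4. Illustrative size for the responder rate.** This rests on assumptions, not on trial data: both eyes on-chart, sham score uniform from 5 to 49 letters, *t* = 3, and a normal between-eye difference with mean 0 to 15 letters and SD 10 to 29.7 letters (29.7 = 0.594/0.02). Two of the simulated results are:

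- Mean 0, SD 29.7: 31.2% respond by letters alone and 33.7% with the *or* rule, a gain of 2.5 points.
- Mean 15, SD 10: 51.9% and 59.7%, a gain of 7.8 points.

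These are the smallest and largest gains over the range. With 36 subjects they amount to 0.025 × 36 = 0.9 and 0.078 × 36 = 2.8, or roughly one to three extra responders if every subject had both eyes on-chart, and fewer otherwise.

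**The case against.** The derivation sections do not contradict one another. Protocol 7.3.1 and SAP 5.4 both lead to one LogMAR value held in the study database, and the endpoint sections may be read as loose shorthand. This largely stands. A reader might infer that two programmers would produce two different primary results. The documents do not support that, because the value is derived once in the eCRF and handed to them.

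A reader might also infer a meaningful loss of precision or power on the primary. The figures do not support that either. Even 0.9% is an upper bound, because off-chart eyes take their LogMAR from a measured distance and are not rounded to chart lines. Nor is the letter score thrown away: it is summarised by treatment group (SAP 9.5.1), and it drives the improvement limb of eye-responder definition 1 and all of definition 2.

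The LogMAR limb also has a proper purpose. Off-chart eyes have no ETDRS score under Protocol 7.3.1, so a letters-only rule could not classify them. That stands. The fault is only that the limb is not confined to those subjects.

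Finally, the number of letters that credits a line is not stated (3 letters on a line defines only on-chart status), and the Ophthalmic Evaluations Manual is not available here. The result in step 3 does not depend on that number. An unrounded Snellen conversion could, however, put some three-line steps slightly off 0.300.

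**Conclusion.** The analysed on-chart LogMAR is not the variable that Protocol 3.1 and SAP 4.1 define. This is a defect of definition with almost no effect on the primary comparison: about 0.3 points of power, or none against plan if 0.594 was itself line-scored.

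The effect worth correcting is on the subject-responder rule. It admits some leads of 11 to 14 letters, although the SAP equates 0.3 LogMAR with 15 letters, and the error runs in one direction only. Eleven letters is the minimum that can qualify, at one starting score in five; it is not the typical responder. This rests on both eyes being on-chart, letters read in order and 0.1 LogMAR per line.

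It would be wrong to infer that the primary conclusion could change by this route. The primary is a mean change with no responder threshold, and SAP 9.5.3 spends all the alpha on it and treats the rest as supportive.

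**What to change.** In SAP 5.4, and in Protocol 7.3.1 at the next amendment:

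- **On-chart eyes:** derive LogMAR from the ETDRS letter score at 0.02 per letter, anchored so that complete lines keep the LogMAR now assigned to that Snellen line. The anchor is needed because 0.02 per letter gives only a slope.
- **Off-chart eyes:** keep the pre-specified count-fingers/hand-motion method. State that it also covers an eye that reads some letters but fewer than 3 on any one line, since SAP 5.4 classes that eye as off-chart.
- **Subject responder:** use the 15-letter limb when both eyes are on-chart, and the 0.3 LogMAR limb only when at least one eye is off-chart.

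Protocol 3.1 and SAP 4.1 then describe on-chart eyes correctly as they stand. The change should be made before the code is broken for the Week 48 analysis.

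No new data are needed, because the letter score is already in the eCRF. The cost is one changed and revalidated derivation, a SAP revision, and protocol wording that goes through the amendment process in Protocol 15. The subject-responder rate will be slightly lower than under the present rule.

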## LogCS

LogCS is obtained based on which lines the subject can read on the chart and the LogCS is then entered in the eCRF.

## Total error score

Total error score is derived by the software and then entered into the eCRF.

## Responder

### Eye Responder

#### Definition 1

Responder at week 48 and also at week 96, will be defined by an improvement of at least 15 letters in the ETDRS score compared to baseline, *or* being greater than a Snellen acuity equivalent of 20/200. Early discontinuations (prior to W48 for the primary endpoint) will be considered as non responder. For week 96 two analyses will be performed: One for completers and one for subjects who don't have the Week 96 value available. If the week 96 ETDRS score is not available, then the previous visit value will be used.

#### Definition 2

Responder, at week 48 and also at week 96, will be defined by having an ETDRS Score equal to or greater than 20 letters. Early discontinuations (prior to W48 for the primary endpoint) will be considered as non responder. For week 96 two analyses will be performed: One for completers and one for subjects who don't have the Week 96 value available. If the week 96 visual acuity score is not available, then the previous visit value will be used.

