3.2 Secondary

- ETDRS visual acuity (quantitative score) over the follow-up period and at Week 96 after IVT injection. Change from baseline of the LogMAR scores will be used for statistical analysis purposes.
- Response status to treatment at Week 48 and 96 after IVT injection. Responder will be defined by an improvement of at least 15 letters in the visual acuity score obtained with ETDRS *or* being greater than a Snellen acuity equivalent of 20/200.
- Measure of parameters of high resolution SD-OCT of the posterior pole and optic nerve at Week 48 and Week 96.
- Measure of the standardized automated visual fields obtained with HVF Analyzer II. Mean Deviation (MD) in decibels of sensitivity will be used at Week 48 and Week 96.
- Measure of contrast sensitivity with the Pelli-Robson chart at Week 48 and Week 96.
- Measure of color vision with the Farnsworth-Munsell 100 Hue color vision test at Week 48 and Week 96.

[REDACTED]

[REDACTED]

[REDACTED]

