5.2 Selection for the Study

5.2.1 Selection Criteria

Subjects must meet all the following criteria at the Screening Visit (Visit 1) in order to be included into the study.

1. Age 15 years or older.
2. Onset of vision loss based on medically documented history or subject testimony, in both eyes for 181 and \leq 365 days in duration.
3. Each eye of the subject maintaining visual ability to allow at least for counting of the examiner's fingers at any distance.
4. Female subjects (if of childbearing potential) must agree to use effective methods of birth control up to 6 months after IVT injection and male subjects must agree to use condoms for up to 6 months after IVT injection.
5. Ability to obtain adequate pupillary dilation to permit thorough ocular examination and testing.
6. Signed written informed consent.

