8.6 Method of Assigning Treatment

The right eye of each subject will be randomly allocated to receive either GS010 or sham treatment in a 1:1 allocation ratio. The fellow (left) eye will receive the treatment not allocated to the right eye. Therefore, each subject will receive GS010 in one eye and sham treatment in the fellow eye. Prior to randomization, each subject's better- and worse-seeing eye will be determined. Efron's minimization method will be used in the randomization process to balance as much as possible the two treatment groups (GS010 and sham) in the better-seeing eyes.

To enroll a subject (Visit 1), the Investigator will call an interactive response system (IRS) and provide brief details about the subject to be enrolled. Each subject will receive a subject number assigned at screening, which will serve as the subject identifier throughout the study. The subject number will be required in all communication between the Investigator (or designee) and the IRS regarding a particular subject. Subject numbers will be tracked via the IRS.

To randomize a subject (Visit 2), the masked Investigator (or designee) will call the IRS and provide brief details about the subject to be randomized. Eligible subjects will be randomized in a 1:1 ratio (right/left eye), taking into account the Efron's minimization method, using the IRS.

The IRS User Guide will describe the steps of the randomization process from the subject's screening up to before IVT injection.

An algorithm with a testing hierarchy will be employed prior to randomization to determine the better- and worse-seeing eye of each subject, as follows:

1. ETDRS visual acuity score for subjects able to read the ETDRS chart. The eye with the higher ETDRS score is the better-seeing eye. For subjects who cannot read the ETDRS chart ("off chart" subjects) a standard study procedure will be used to determine visual acuity based on counting fingers at a given distance. The eye with the best visual acuity based on this method is the better-seeing eye. If one eye of a subject is able to read letters on the ETDRS chart and one eye cannot, the eye able to read the ETDRS chart is the better-seeing eye.
2. SD-OCT parameters (to be used if there is no inter-eye difference based on Criterion 1):

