12.4.2 Secondary Analysis

The treatment estimate at Week 96 will be based on the same statistical approach as the primary endpoint analysis. Another analysis will compare time course of the response up to Week 96 using the mixed model procedure. The responder analyses at both Week 48 and Week 96 will be based on a McNemar test for paired samples. To verify whether the treatment effect is dependent upon the better-seeing eye or the worse-seeing eye at study entry, a test of homogeneity of subgroups (better-seeing or worse-seeing eye treated) effects in stratified paired binary data ([Zhao 2014](#)) will be performed.

Like the primary endpoint, a meta-analysis will be performed combining both studies (GS-LHON-CLIN-03A (RESCUE) and study GS-LHON-CLIN-03B (REVERSE)). A conditional logistic model will be used to assess the effect of better- and worse-seeing eye at study entry and the effect of time from onset of disease and the effect of treatment.

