## Secondary Objectives:

- To assess the effect of GS010 on parameters measured with high resolution spectral-domain optical coherence tomography (SD-OCT), including Retinal Ganglion Cell (RGC) layer, inner and outer nuclear layer (INL and ONL) thickness/volume, Retinal Nerve Fiber Layer (RNFL) thickness and topographical map analysis of these anatatomical regions.

- To evaluate the efficacy of GS010 compared with sham on the visual acuity (LogMAR) in a dynamic perspective through the comparison of the time course of the response.
- To verify whether the efficacy at Week 48 and at Week 96 of GS010 compared with sham and measured by the change from baseline of the LogMAR is dependent upon the treatment of the best- or worst-seeing-eye.
- To verify whether the rate of responders at Week 48 and 96 is dependent upon the treatment received and whether the magnitude of the treatment effect is dependent upon the treatment of the best- or worst-seeing eye at entry.
- To assess the effect of GS010 on standardized automated visual fields obtained with the Humphrey Visual Field (HVF) Analyzer II.
- To assess the effect of GS010 on contrast sensitivity measured with the Pelli-Robson chart.
- To assess the effect of GS010 on color vision measured with the Farnsworth-Munsell 100 Hue color test.

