### Eye responders

The responder analyses at both Week 48 and Week 96 will be based on a McNemar test comparing all-GS010 eyes against all-Sham eyes.

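### The protocol's homogeneity test of better- versus worse-eye dependence in responders mixes the entry difference between eyes into the interaction it is meant to test

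*SAP*

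**What the plan says.** **Definition.** Protocol 3.2 states "Responder will be defined by an improvement of at least 15 letters in the visual acuity score obtained with ETDRS" and adds, joined by 'or', an acuity-level limb. SAP 5.4 (Eye Responder, Definition 1) repeats both limbs; the second is "being greater than a Snellen acuity equivalent of 20/200" at the visit, with no reference to baseline.

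**Eye status.** Protocol 8.6 sets it before randomization, first by entry acuity: "The eye with the higher ETDRS score is the better-seeing eye". OCT and contrast sensitivity only break ties.

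**Entry.** Protocol 5.2.1 sets an acuity floor, "Each eye of the subject maintaining visual ability to allow at least for counting of the examiner's fingers at any distance". No selection or inclusion criterion sets a ceiling.

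**Test.** Protocol 12.4.2 plans "a test of homogeneity of subgroups (better-seeing or worse-seeing eye treated) effects in stratified paired binary data", known only by citation. SAP section 2 keeps the objective, "whether the magnitude of the treatment effect is dependent upon the treatment of the best- or worst-seeing eye at entry", but for eye responders SAP 9.5.5 lists only "a McNemar test comparing all-GS010 eyes against all-Sham eyes".

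**Contrast.** The LogMAR interaction model in protocol 12.4.1 has an eye-status main effect beside the interaction. The responder homogeneity test describes no counterpart.

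**The concern.** The variable that splits the subjects (which eye saw better at entry) and the level limb of the response rest on the same quantity. An eye already above 20/200 at entry is a responder if it stays as it was, or if it loses letters but remains above. Such eyes are more often the better-seeing one.

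With no drug effect, subjects with the better eye treated therefore tend to show GS010 ahead, and subjects with the worse eye treated tend to show sham ahead. A test comparing these two paired effects reads that pattern as dependence on the eye treated. The error has one direction: it suggests benefit when the better eye is treated and can hide benefit confined to worse-seeing eyes. Which eye benefits is a stated secondary objective, and SAP 9.5.1 makes the best-seeing eye the basis of the FDA primary analysis, so the answer will be read with interest.

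**Working it through.** **1. What the test estimates.** Let pB and pW be the responder rates of better- and worse-seeing eyes without treatment, β = pB − pW, and tB, tW the treatment effects in each.

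- Better eye treated: (pB + tB) − pW = tB + β
- Worse eye treated: (pW + tW) − pB = tW − β
- Difference: (tB − tW) + 2β

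The quantity of interest is tB − tW. Homogeneity of the paired effects tests it only if β = 0, and the level limb makes β positive.

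**2. Inputs for size.** The plan gives no size or power for this test. Its only sample-size figure concerns the paired LogMAR comparison and reproduces: ((1.960 + 1.036)/0.50)² = 35.9, so 36 subjects. Borrowed or assumed:

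- Entry letters: lognormal from the planning mean 23.4 and SD 28.3 (protocol 12.2). σ² = ln(1 + (28.3/23.4)²) = 0.901, σ = 0.949, μ = ln 23.4 − 0.451 = 2.702. This is a proxy, not this trial's entry distribution.
- 20/200 taken as 35 letters (assumption). P(>35) = 18.4%; by eye status at correlation 0.7, 26% of better and 10% of worse eyes.
- SD of change per eye: 0.594/√2 LogMAR (SAP 3.3, eyes independent) × 50 letters per LogMAR (SAP 5.4: 15 letters = 0.3) = 21. An SD of 10 is a pure assumption.
- 18 subjects with each eye status treated; fellow-eye correlation 0.7 or 0.9 (assumption).
- Stand-ins for the cited test: Wald (difference of mean paired differences over √(s₁²/18 + s₂²/18)) and Fisher's exact test on discordant pairs by stratum.

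**3. Rejection with no treatment effect, nominal 5%, 20,000 trials.**

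| SD | Correlation | Responders, better / worse eyes | Wald | Exact |
|---|---|---|---|---|
| 21 | 0.7 | 41% / 31% | 19% | 9% |
| 21 | 0.9 | 39% / 33% | 11% | 4% |
| 10 | 0.7 | 32% / 17% | 49% | 24% |
| 10 | 0.9 | 29% / 20% | 25% | 7% |

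The algebra shows in the first row: β is about 0.10, the paired effects are +0.10 and −0.10, and their difference is 0.21 = 2β before rounding. The exact McNemar test rejects in about 2% throughout.

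**4. Dependence on entry acuity (correlation 0.7, exact / Wald).** If 7.5% of eyes enter above 20/200: 4% / 10% at SD 21 and 6% / 22% at SD 10. If 2.5% do: 2% / 7% and 1% / 10%.

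**5. A real effect hidden.** Give 15 letters to treated worse-seeing eyes only (SD 21, correlation 0.7). The true interaction is −0.255, but the paired effects are +0.106 (better eye treated, where GS010 does nothing) and +0.149. The test sees 0.106 − 0.149 = −0.043 and rejects in 7% (Wald). At SD 10 it rejects in 14%.

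**6. Separating eye status.** Compare GS010 with sham among better eyes, then among worse eyes, and subtract:

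[(pB + tB) − pB] − [(pW + tW) − pW] = tB − tW

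β cancels. Rearranged, this is the mean number of responding eyes per subject (0, 1 or 2) in better-eye-treated subjects minus the same mean in worse-eye-treated subjects: (pB + tB + pW) − (pB + pW + tW). A two-sample test on that count takes the subject as the unit and so respects the within-subject correlation. In reruns it rejected in 4% to 6% with no effect, with both eyes losing 10 letters, and with an equal 15-letter effect in both eyes.

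**The case against.** **Narrow target.** The test appears once, in the protocol. Protocol 12.1 leaves methodological detail to the SAP, and SAP 9.5.5 does not restate it. SAP 9.5.3 makes everything beyond the primary endpoint supportive. All of this stands and limits the weight of the point. But the SAP keeps the objective and withdraws nothing, so either the protocol's test applies or the responder objective has no method.

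**Cover elsewhere.** LogMAR dependence is analysed with baseline or eye status in the model (SAP 9.5.1, 9.5.5). Protocol 12.4.2 also plans a conditional logistic responder model, pooled with RESCUE, with an eye-status term that would absorb β. That is partial cover: no interaction term is stated, and it concerns the pooled data.

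**Uncertain size.** The cited test's formula is not in the documents, and the stand-ins differ about twofold or more. Wald is itself somewhat liberal here, near 7% when the artefact has almost gone. The largest rates need the assumed SD of 10. This stands. Off-chart eyes do not rescue the test: setting 20% to 60% of the lowest eyes to 0 letters left Wald at 19% to 20% (SD 21) and 50% (SD 10).

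**Stronger readings not supported.** A reader might infer that the responder analyses as a whole are biased. They are not: about half the treated eyes are better eyes, and McNemar keeps its size. A reader might extend the point to Definition 2, "will be defined by having an ETDRS Score equal to or greater than 20 letters". That definition is a pure level, but it exists only in the SAP and no homogeneity test is planned on it. A reader might also conclude that response must be redefined so that eyes already above 20/200 cannot count. That would stop reflecting preserved vision, although SAP 9.5.1 names halting acuity loss as a benefit. Nor would it suffice: with entry uniform on 0 to 34 letters no eye starts above the threshold, the two definitions coincide, and Wald still rejects in 8% to 9% (SD 21) or 13% (SD 10), although the exact stand-in stays at 3%. The fault lies in the contrast, not in Definition 1.

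**Conclusion.** The concern holds for Definition 1 and for this one test. The paired homogeneity comparison assesses 2β plus the true interaction, and the level limb makes β positive because eye status is set by entry acuity and entry has no ceiling. That part is algebra and needs no assumption beyond some eyes entering near or above 20/200.

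The size is illustrative. With no effect, Wald rejection is 19% to 11% at SD 21 and 49% to 25% at SD 10 as fellow-eye correlation goes from 0.7 to 0.9; the exact stand-in gives 9% to 4% and 24% to 7%. These rates rest on a planning distribution as entry proxy, 35 letters for 20/200, and stand-ins for a test the documents do not describe. If almost no eye enters near or above 20/200, little problem remains. The documents do not show that this trial will report a false dependence, only that the test as planned cannot tell one from a real one. The primary analyses are untouched. This is a cheap correction to a supportive analysis, worth making.

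**What to change.** Keep Definition 1 unchanged. In protocol 12.4.2, and in SAP 9.5.5 under Eye responders, replace the homogeneity test with wording such as: 'Dependence on the eye treated will be assessed by the eye-status-by-treatment interaction: the GS010-minus-sham difference in responder rate among better-seeing eyes minus the same difference among worse-seeing eyes, allowing for within-subject correlation. It will be tested by comparing the number of responding eyes per subject (0, 1 or 2) between better-eye-treated and worse-eye-treated subjects with a permutation test.' This matches the Best and Worst comparisons already in SAP 9.5.1.

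Optionally, tabulate Definition 1 responders by arm and by whether the eye was already better than 20/200 at baseline, so that gain and maintenance can be told apart.

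**Cost.** One sentence in each document and perhaps one table; no new data. Protocol Appendix V bars SAP amendments once the randomization code is broken, so it must be done before then. The contrast is between subjects, about 18 against 18, and power is limited: a 15-letter effect in worse-seeing eyes only is detected in about 17% to 18% at SD 21 and 42% at SD 10, against 7% and 14% as written. A non-significant result should not be reported as evidence that the effect is the same in both eyes. The interaction is on the responder-rate scale, so equal gains in letters need not give exactly equal differences in rates; in the reruns that shift was small (0.03 to 0.05).
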